# **Secondary Analyses**

We will assess differences in plasma metabolites using a linear mixed model approach with random intercepts, in which the log-transformed metabolite will be regressed on treatment type (Placebo vs Coenzyme Q10 or NR), time point (pre vs post) and the interaction of the two. We will use metaboanalyst to conduct pathway enrichment analysis.

For differential analysis of transcriptomic data, paired analyses of pre- and posttreatment with NR or CoQ10 compared to pre- and post- treatment with placebo will be performed using Significance Analysis of Microarrays (SAM) method implemented in Multi Experiment Viewer (MeV) application (Saeed et al. 2006; Saeed et al. 2003). Genes differentially expressed between two groups with a q-value (False Discovery Rate) below 0.05 were considered significant.

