# SCHEMA

# **1.0 INTRODUCTION**

# 1.1 Background and Prior Research

**Sarcopenia is a common complication of chronic kidney disease.** Sarcopenia is defined by decreased muscle mass or function and is central to the frailty phenotype that is associated with disability, hospitalization, and death. Studies have shown that altered metabolism in CKD leads to well-described catabolic and pro-inflammatory processes with adverse consequences for lipid, amino acid, and protein metabolism that are linked to overall energy metabolism^5. These events consequently lead to an impaired insulin response, contributing to significant comorbidity among patients living with CKD.

**Sarcopenia alters glucose metabolism**. Insulin resistance in CKD can contribute to catapleurosis, which in turn increases reliance on the muscle amino acid pool for mitochondrial tricarboxylic acid-cycle respiratory fuel. These events culminate, ultimately, in muscle breakdown, sarcopenia, weakness and fatigue, increasing risk of mobility, disability and frailty.

**CKD and sarcopenia alter metabolic pathways.** Metabolomic profiling of CKD compared to controls under conditions of fasting and insulin clamp testing reveal marked aberrancy in CoQ10 biosynthesis pathways and niacinamide metabolism respectively. This suggests impaired mitochondrial metabolism as a major contributor in insulin resistance (figure 1). We have observed fasting-state pathway differences in ubiquinone (Coenzyme Q) biosynthesis among patients with CKD compared to controls, suggesting alteration in the integrity or efficiency of the electron transport chain (ETC) of the mitochondria, in turn predisposing to mitochondrial oxidant production resulting in insulin resistance.

**Deficiency in CoQ10 levels has been associated with oxidative stress and impaired oral glucose tolerance in pre-clinical models**. This may explain the observed uncoupling of muscle mitochondrial oxidative phosphorylation and oxidative stress in CKD. CoQ10 administration in advanced kidney disease patients improved oxidative stress with reduction in isofuran levels (products of lipid peroxidation). However, little is known about its effects on oxidative stress and mitochondrial function via assessment of mitochondrial bioenergetics using high throughput respirometry assessments in moderate-sever CKD not requiring dialysis.

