# 2.0 STUDY OBJECTIVES AND DESIGN

# 2.1 Primary Objectives

The primary objectives of this study are to:.

- To test if NR or CoQ10 supplementation improves aerobic capacity by cycle ergometry testing compared with placebo.
- To test if NR or CoQ10 improves muscle work efficiency by bicycle ergometry

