# 2.2 Secondary Objectives

The secondary objectives of this study are to:

- To test if NR or CoQ10 improves peripheral blood monocyte bioenergetics health.
- To test the effects of oral NR or CoQ10 supplementation on metabolic response profile.
- To test if NR or CoQ10 supplementation reduces inflammatory and oxidative stress biomarkers.
- To test if NR or CoQ10 improves subjective fatigue, self-reported physical function, and chart failure symptoms.

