# 2.3 Study Design

**Overview of study design:** This is a placebo-controlled, double-blind crossover trial with 3 arms: placebo, NR, and CoQ10. There are 2 phases 56 days each separated by a 1-week washout period.

A brief screening visit will assess eligibility criteria, and will include informed consent. Qualified participants will be randomly assigned (1:1) to 56 days of placebo followed by 7 days NR or CoQ10, followed another 7 day washout followed by 56 days of either NR or CoQ10. Qualified participants will participate in at least 4 study visits, plus a screening visit. An optional P MRS study visit to assess in vivo muscle mitochondrial phosphorylation capacity will be offered to those who qualify. Including the separate MRS visit will increase the total visits to 8. Study outcomes will be assessed at each of these 4 major visits.

Subjects will receive 1000mg of Nicotinamide riboside (Tru Niagen) or coenzyme Q10 (1200mg/day) for 8 weeks. This dose was chosen based on a review of studies in the literature evaluating biological activity. Placebo will consist of identical appearing tablet.

Objectives	Population	Exposure	Design	Outcome
Primary- To test if NR or CoQ10 supplementation improves aerobic capacity and muscle performance	Mod-severe CKD with eGFR < 50 mL/dL (N=30)	Randomized order CoQ10 or NR or Placebo	Placebo-controlled double-blind control crossover	VO2max and Work efficiency
Secondary- To test NR or CoQ10 on descriptive measures of mitochondrial and metabolic functioning	Mod-severe CKD with eGFR < 50 mL/dL (N=30)	Randomized order CoQ10 or NR or Placebo	Placebo-controlled double-blind control crossover	
 
-monocyte bioenergetics (Reserve capacity)
 
-ATPmax (MRS Imaging)
 
-Blood metabolomics & biomarkers
 
-Fatigue & Heart questionnaires
 

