# 7.6 Data Analysis

# 7.6.1 Primary Analyses

The major assumption in the cross-over trial is that there is no carryover effect of first period into the second period. The assumption is that a 1-week washout combined with a 2 month treatment will be sufficient to eliminate any potential carryover effect. The statistical model we assumed for continuous data from the  $3 \times 3$  crossover trial. We will use ANOVA to estimate sequence effects, treatment effects, and period effects. Given the short half-life of these drugs, we estimate that the drug washout will occur over 1 week with any residual effects by 3 weeks. According to this model, the coefficient of the interaction term between the treatment and time represents the treatment effect.

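### The metabolite and transcript analyses do not say whether NR and CoQ10 are each compared with placebo or pooled, and the metabolite model lists no period term

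*Combined protocol and SAP*

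**What the plan says.** Section 2.3 describes the design: "This is a placebo-controlled, double-blind crossover trial with 3 arms: placebo, NR, and CoQ10". Table 2 in section 7.3 has six sequences of five, so each participant takes all three treatments.

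The Secondary Analyses section (numbered 7.6.2 only in the table of contents) gives two analyses:

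- **Metabolites.** A linear mixed model with random intercepts, the log metabolite being "regressed on treatment type (Placebo vs Coenzyme Q10 or NR), time point (pre vs post) and the interaction of the two", followed by pathway enrichment. No error-rate rule is written for metabolites.
- **Transcripts.** The comparison is "paired analyses of pre- and posttreatment with NR or CoQ10 compared to pre- and post- treatment with placebo", with this threshold: "Genes differentially expressed between two groups with a q-value (False Discovery Rate) below 0.05 were considered significant".

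Neither paragraph states how many levels treatment has, names a contrast, or mentions period. Section 7.6.1, for the same three-period crossover, uses ANOVA to estimate "sequence effects, treatment effects, and period effects".

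The secondary objective in section 2.2 reads: "To test the effects of oral NR or CoQ10 supplementation on metabolic response profile". Section 5 and Table 1 schedule blood and mRNA samples at one baseline visit and at visits 2, 3 and 4, each at the end of a treatment period. No sample is scheduled after a washout.

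**The concern.** The metabolite wording has one 'vs' with two sides, and the transcript wording ends in two groups. A programmer could follow both to the letter and code NR and CoQ10 as a single active level. The estimate would then be the average of two products for which the protocol gives partly different rationales. A feature moved by one product would be diluted, features moved in opposite directions would cancel, and an enriched pathway could not be traced to either product.

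Leaving the coding open is also a weakness in itself. With many features, an analyst who has seen the data could choose whichever coding yields more hits.

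The missing period term is a second gap in the same model. Three post-treatment visits spread over about 20 weeks can differ for reasons unrelated to treatment, and the pre/post term does not separate them.

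**Working it through.** **1. The plan's own figure.** The only sizing is Table 3, for VO2max. A paired t test (noncentral t, n − 1 degrees of freedom, two-sided 0.05) gives 34 / 16 / 10 participants for 0.5 / 0.75 / 1 SD at 80% power, and 44 / 21 / 13 at 90%. Every cell matches. This fixes the unit used below, the SD of a within-person difference between two treatments. The documents give no effect size for metabolites or transcripts, so those below are assumptions.

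**2. Separate and pooled contrasts.** Inputs: n = 30 per treatment (Table 2) and equal, independent within-person errors with variance s² (assumption).

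- One product minus placebo: variance s²(1/30 + 1/30) = 0.0667 s².
- Mean of the two products minus placebo: variance s²(1/30 + 1/60) = 0.05 s².
- Variance ratio: 0.05 / 0.0667 = 0.75.

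If only one product acts, with effect δ, the pooled contrast estimates δ/2. The ratio of z-values is 0.5 / √0.75 = 0.577. The sample size needed for equal power rises by 0.75 / 0.25 = 3.

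By the normal approximation:

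- 80% power: non-centrality 2.80 × 0.577 = 1.62, power about 37%.
- 90% power: non-centrality 3.24 × 0.577 = 1.87, power about 46%.

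**3. Power for one feature.** Crossover model, n = 30, residual degrees of freedom 90 − 1 − 29 − 2 − 2 = 56, two-sided 0.05. Non-centrality is d√30 for a separate contrast and (mean of the two effects) × √(30/0.75) for the pooled one. At 0.5 SD with one product active these are 2.74 and 1.58.

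| Effects (NR, CoQ10) in SD | Separate, active product | Pooled |
|---|---|---|
| 0.5, 0 | 76.8% | 34.3% |
| 0.75, 0 | 98.1% | 64.5% |
| 1, 0 | >99.9% | 87.4% |
| 0.5, −0.5 | 76.8% each | 5.0% |
| 0.5, 0.5 | 76.8% each | 87.4% |

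If the two separate tests share the error rate at 0.025 each, power is 66.8% at 0.5 SD and 96.2% at 0.75 SD.

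**4. Period.** Counting Table 2 by sequence names, each treatment falls 10 times in each of periods 1, 2 and 3. For simple treatment means, the bias in NR minus placebo is the sum over periods of (share of NR observations in that period − share of placebo observations in that period) × period effect. With 10/30 everywhere, each bracket is zero. The contrast is then unbiased, and the period variation goes into the residual. When participants leave, the shares can differ and the sum need not be zero. The documents give neither a period effect nor drop-out by sequence, so this bias cannot be sized.

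**5. Pre and post.** With one baseline value b used for every treatment, (NR − b) − (placebo − b) = NR − placebo. The interaction then reduces to a comparison of post-treatment values. If the preceding visit were used as 'pre' instead, that sample would have been taken while the participant was still on the previous treatment, according to section 5. The text does not say which is meant.

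**The case against.** The strongest reply is that the plan never says the products are pooled. Throughout the objectives, 'or' means either product, as in the primary one: "To test if NR or CoQ10 supplementation improves aerobic capacity by cycle ergometry testing compared with placebo". The design statement in section 7.1 uses it the same way. If 'or' meant pooling, the primary objective would be pooled too, yet section 2.3 has three arms and section 7.6.1 refers to a 3×3 crossover. A paired comparison of two groups also fits one active period against placebo more naturally than two active periods against one. A three-level factor has an interaction with time as well, so that wording settles nothing.

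This stands, and a reader should not infer that the plan pools. It does not close the gap: no contrast is named, and other sections waver as well. Section 7.3 calls the trial both a three-treatment and a two-treatment crossover, and section 7.4 refers to two treatment groups.

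Three further replies have force:

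- Pooling is not always harmful. Equal effects in the same direction gain power (87.4% against 76.8%), and sections 1.2 and 1.3 give both products a shared mitochondrial rationale.
- The background finding of "marked aberrancy in CoQ10 biosynthesis pathways and niacinamide metabolism respectively" concerns fasting and insulin-clamp conditions in CKD against controls. It makes product-specific profiles plausible, particularly with the NAD+ rationale for NR in section 1.1, but does not show that the products act differently.
- Table 2 is balanced, so omitting period does not bias the contrasts as designed. Recruiting up to 36 (section 4.3) offsets losses overall but does not guarantee balance within each sequence.

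**Conclusion.** The point holds as a gap in specification. The Secondary Analyses text leaves the treatment coding and contrasts undefined and permits a pooled active group. Under pooling with only one product active, the effect halves, z falls to 58%, and an illustrative 80% power becomes about 37%. Opposite effects cancel and similar effects gain power. In every pooled case a hit cannot be assigned to a product. These figures assume 30 completers, equal independent errors and single-feature testing at 0.05; the loss at FDR thresholds was not computed.

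The missing period term is a firmer finding about the metabolite model as written: it differs from the primary analysis of the same crossover. Its cost is mainly precision while the sequences stay balanced, with possible bias of unknown size under drop-out.

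A reader might go further and conclude that the metabolic objective cannot be answered for either product. The documents do not support that, because it follows only if pooling is assumed. The point concerns secondary analyses and leaves the VO2max endpoint untouched.

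**What to change.** In the Secondary Analyses section:

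1. Code treatment as a three-level factor. Report NR–placebo and CoQ10–placebo separately for every metabolite, gene and enrichment run, with one paired comparison per product for transcripts.
2. Add period as a fixed effect to the metabolite model and keep the participant random intercept.
3. Compare post-treatment values by treatment, with the single baseline as reference or covariate, and do not assume a 'pre' sample for each period.
4. State FDR control across features and both contrasts, for metabolites as well as genes.
5. Label any pooled contrast supplementary.

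The cost is wording and twice as many contrasts under FDR control. As a guide, two tests at 0.025 each give 66.8% power where one at 0.05 gives 76.8%, at an assumed 0.5 SD. That is still above the 34.3% of a pooled test when only one product acts. No new data are needed.

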# Blood Collection:

- NAD samples will be obtained from fasting whole blood collected in one 2.7ml Blue (sodium citrate tube). From the blue tube, after inversion mixing, 0.5ml will be pipetted into 2 cryotubes **on dry ice.** Samples will be immediately frozen on dry ice and placed in -80C ASAP. Samples will be sent to [name] in clinical pharmacology ([contact]).
- EDTA Plasma samples will be sent to University of California at Davis West Coast Metabolomics for liquid chromatography high-resolution mass spectrometry (LC-MS) for targeted metabolomics analysis. We will perform additional transcriptomics using mRNA samples obtained from Paxgene tubes which will also be sent to West Coast Metabolomics.
- Paxgene mRNA will be obtained at baseline and post-intervention visits.
- Clinical laboratory assays for determination of comprehensive metabolic panel (electrolytes, blood urea nitrogen, creatinine, glucose, albumin, total protein, calcium, alkaline phosphatase, ALT, AST, total bilirubin), CPK, lactate, triglyceride will be performed at the *KRI Core Research laboratory*.

*Urine collection:* **Spot urine** for metabolomics will be collected at baseline and after each treatment period (visits 2-4).

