# Week 6, 13, 20 (Visit 2, 3, 4):

The prevention center and [name] lab will be contacted to arrange the primary outcome of resting energy expenditure, aerobic capacity and secondary outcomes of monocyte mitochondrial energetics at the end of each treatment period. Patients will also have fasting blood collection and return a 24hr urine collection. If qualified, they will also receive a repeat MRS at UWMC during the same week. **Patient remain on treatment during these visits to ensure drug effect.** 

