# Washout (week 7 and 14):

After the second visit, the participant will undergo a 1 week washout period prior to initiating the subsequent treatment arm for another 6 week period.

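### The metabolite and transcript analyses need a pre-treatment value for each treatment, but periods 2 and 3 have no pre-treatment sample, so that value is undefined there

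*Combined protocol and SAP*

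**What the plan says.** Under Secondary Analyses (7.6.2 in the table of contents), each log-transformed metabolite is regressed, with random intercepts, on "treatment type (Placebo vs Coenzyme Q10 or NR), time point (pre vs post) and the interaction of the two". For gene expression, "paired analyses of pre- and posttreatment with NR or CoQ10 compared to pre- and post- treatment with placebo will be performed", using SAM, and genes with a "q-value (False Discovery Rate) below 0.05" are declared significant. Metabolite results also go into a pathway enrichment analysis.

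The sampling plan is in Section 5.0. Under Blood Collection, "Paxgene mRNA will be obtained at baseline and post-intervention visits". Table 1 and Table 4 give the same four occasions for blood and urine: baseline and the end of each treatment period (weeks 6, 13 and 20). At visits 2 to 4, "Patient remain on treatment during these visits to ensure drug effect". The washouts fall in weeks 7 and 14: "After the second visit, the participant will undergo a 1 week washout period prior to initiating the subsequent treatment arm". Table 1 has the next product dispensed at visits 2 and 3, and no visit at the end of a washout. Section 8.2 counts four blood draws.

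**The concern.** Three treatments analysed by pre and post values need three pre-treatment values per participant. The plan collects one, at baseline. For the treatments given in periods 2 and 3, nothing in the documents says which sample is the pre-treatment one.

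The possible choices give different estimates, standard errors and lists of significant metabolites, and the plan does not choose among them. The analyst would have to, possibly after seeing the data. The metabolic response profile is a stated secondary objective and endpoint, so the choice matters to a reported result.

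**Working it through.** **1. Are four draws really all that is planned?** Section 9.1 gives about 60 mL per visit and about 245 mL in total. Table 4 gives 3 + 4 = 7 mL at screening.

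- Four draws: 4 × 60 + 7 = 247 mL, which reproduces the stated 245 mL.
- Six draws (adding one after each washout): 6 × 60 + 7 = 367 mL, which does not.

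The stated volume confirms that no post-washout draw is planned.

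**2. Previous visit as the pre-treatment value (baseline in period 1).** Let *a* and *b* be the true NR and CoQ10 effects against placebo. Assume no carryover and the six equal sequences of Table 2 in Section 7.3.

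| Sequence | NR change | Placebo change | Difference |
|---|---|---|---|
| Placebo-CoQ10-NR | a − b | 0 | a − b |
| Placebo-NR-CoQ10 | a | 0 | a |
| NR-Placebo-CoQ10 | a | −a | 2a |
| NR-CoQ10-Placebo | a | −b | a + b |
| CoQ10-Placebo-NR | a | −b | a + b |
| CoQ10-NR-Placebo | a − b | −a | 2a − b |

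The mean NR change is a − b/3 and the mean placebo change is −(a + b)/3. The contrast is 8a/6 = 4a/3, a 33% overstatement whatever *b* is. By symmetry CoQ10 gives 4b/3. For metabolites this is on the log scale. Period effects cancel by balance.

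Standard errors, with residual SD 1 (assumed), independent errors and n = 30:

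- True: the two changes share a visit in four sequences (variance 1 + 4 + 1 = 6) and share none in two (variance 4). The mean variance is (4 × 6 + 2 × 4)/6 = 5.33, and √(5.33/30) = 0.42.
- Mixed model: the six rows hold baseline once, visits 2 and 3 twice each and visit 4 once. The expected residual mean square is (6 − 10/6)/5 = 0.867, and √(4 × 0.867/30) = 0.34, which is too small.

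Simulation, 6,000 trials per setting, covered between-person SD 0.5, 1 and 3, drift 0 or 0.3 per period, and a CoQ10 effect of 0 or 1. With no NR effect, the mixed model rejected in 10 to 13% of trials at a nominal 5%. A paired test of changes rejected in about 4 to 5%. With a true NR effect of 0.5, both averaged 0.67.

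**3. The single baseline reused for all three treatments.** (NR − baseline) − (placebo − baseline) = NR − placebo, so the baseline cancels.

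- True SE: √(2/30) = 0.258.
- Mixed model: three copies of baseline are counted as independent rows. The residual mean square is (6 − 12/6)/5 = 0.8, and √(4 × 0.8/30) = 0.327. The ratio is √1.6 = 1.26, so the SE is 26% too large.
- Simulation: estimate 0.502 for a true 0.5; false positives about 1.6%; power at 0.5 SD about 30%, against 47 to 48% for the direct comparison.
- A paired test of changes is identical to the end-of-period comparison and holds about 5%.

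**4. Baseline entered once, as the pre-treatment value of the period-1 treatment only.** The interaction is unbiased, but its SE is about 0.6 SD (0.58 to 0.60 simulated) against 0.26.

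**5. End-of-period values compared directly.** The SE is √(2/30) = 0.258 SD. Simulation of the model with period and participant terms gave 1.01 for a true 1.0, SE 0.26 and about 6% false positives (Monte Carlo error about 1 point). Adding post-washout draws and analysing changes would give √(4/30) = 0.365 SD, which is worse.

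**The case against.** The strongest reply is that the documents call visits 2 to 4 post-treatment or post-intervention visits and keep baseline separate. In that vocabulary the pre-treatment value is baseline and reading 3 applies. The transcript analysis, run as paired within participant, is then already the right one. This stands: the baseline reading is the more natural, and the 4/3 factor describes a choice that no section states.

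It does not close the point. The metabolite model under the baseline reading still needs a decision on how one sample becomes the pre-treatment row of three treatments, and the two ways worked out above are both inefficient. Nor is the previous-visit reading excluded, since in a crossover the preceding sample is a common choice of period baseline.

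A reader might infer three stronger things that the documents do not support:

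- *That every way of filling the gap gives wrong results.* A reused baseline gives the right estimate, and a valid paired transcript test.
- *That the gene list will contain too many false positives.* Paired tests hold about 5% under either reading. The 4/3 factor enlarges a true effect and creates none: with no NR effect, the differences in the table average to zero.
- *That the primary VO2max analysis fails in the same way.* Section 7.6.1 also calls a treatment-by-time interaction the treatment effect, but it specifies an ANOVA with treatment, period and sequence effects. That wording needs aligning; it does not show that the analysis is invalid.

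The MRS text mentions visits 2, 4 and 6, but Table 1 has no visit 6 and that text adds no blood or RNA sample.

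**Conclusion.** The point holds. The plan states a pre/post method for each treatment, and its sampling supplies a pre-treatment value only for the treatment given first. For metabolites, each of the three ways of filling the gap costs something: a contrast 33% too large with about 10 to 13% false positives, a standard error about 26% too large, or one more than twice as large as necessary (about 0.6 against 0.26 SD). For transcripts, the previous-visit reading overstates the effect by a third, while the baseline reading is sound if the test is paired within participant.

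The 4/3 factor and the cancellation of a common baseline do not depend on variance components. The 4/3 factor does need complete, balanced sequences and no carryover. Section 4.3 expects drop-out, and unbalanced sequences would let one drug's effect leak into the other's contrast under the previous-visit reading. The standard errors assume independent residuals of equal variance. The error rates and power come from simulations with assumed variance components, which the documents do not give.

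Metabolomics is a secondary endpoint, and transcriptomics is an additional analysis absent from the endpoint lists in Section 7.2. The point therefore ranks below one that changes the primary result, but it should be settled before the data are analysed.

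**What to change.** In Secondary Analyses, replace the pre/post-by-treatment interaction. Compare the end-of-period values (visits 2, 3 and 4) within participant, with terms for treatment and period and a random participant intercept. For transcripts, run SAM as two paired comparisons: end of NR against end of placebo, and end of CoQ10 against end of placebo. State that baseline is entered at most once and that no on-drug visit serves as a pre-treatment value. Align the treatment-by-time sentence in Section 7.6.1 in the same way.

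The cost is a change of wording in two sections, with no new sample, visit or participant.
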